## 9.2.2.1.2. Setting for Concurrent Comparator RCA

Individuals must meet all of the following inclusion criteria to be eligible for inclusion in the concurrent comparator RCA study:

- 1. ABRYSVO vaccination (exposure ascertainment further described in Section 9.2.3.1) from 22 October 2024 through the most recent data available at study commencement.
- 2. Individuals aged 18 to 59 years old at ABRYSVO vaccination.
- 3. At least 365 days of continuous enrollment in medical and pharmacy claims prior to and including the day of ABRYSVO vaccination, with gaps of up to 45 days in coverage permitted.
- 4. Not pregnant, defined as no diagnosis or procedure codes for a pregnancy marker in the 42 weeks prior to ABRYSVO vaccination through and including the day of ABRYSVO vaccination AND no diagnosis or procedure codes for a pregnancy outcome on the day of

ABRYSVO vaccination through up to the 42 weeks (as data is available) after ABRYSVO vaccination.

[figure not shown]
- 5. No receipt of AREXVY (RSV vaccine, adjuvanted) or other non-Pfizer RSV vaccine during the 365 days pre- or 84 days (as data is available) post-vaccination.
- 6. No code for GBS or its sequalae, in any setting or position, in the 365 days prior to and including ABRYSVO vaccination.

There are no exclusion criteria for this analysis.

#### 9.2.2.2. Setting for SCRI

The study population for the SCRI study will be non-pregnant individuals 18-59 years who received an ABYRSVO vaccination from 22 October 2024 through the most recent data available at the time of the study commencement (Figure 2). The primary analysis for the SCRI study will not require vaccinees to meet the algorithm definition for increased risk of RSV-LRTD due to concerns with misclassification (i.e., not everyone with one of these conditions will be identified as such via the claims-based algorithm), but vaccinees will be presumed to be at increased risk of RSV-LRTD because this is the indication for ABRYSVO. A secondary analysis (Section 9.2.7.2) will restrict to the population who meet the algorithm definition (Table 3).

Figure 2. SCRI study design

Individuals must meet all of the following inclusion criteria to be eligible for inclusion in the SCRI study:

- 1. ABRYSVO vaccination (exposure ascertainment further described in Section 9.2.3.1) from 22 October 2024 through the most recent data available at the time of the study commencement.
- 2. Individuals aged 18 to 59 years old at ABRYSVO vaccination.

- 3. At least 365 days of continuous enrollment in medical and pharmacy claims prior to and including the day of ABRYSVO vaccination, with gaps of up to 45 days in coverage permitted.
- 4. Not pregnant, defined as no diagnosis or procedure codes for a pregnancy marker in the 42 weeks prior to ABRYSVO vaccination through and including the day of ABRYSVO vaccination AND no diagnosis or procedure codes for a pregnancy outcome on the day of ABRYSVO vaccination through up to the 42 weeks (as data is available) after ABRYSVO vaccination.
- 5. No receipt of AREXVY (RSV vaccine, adjuvanted) or other non-Pfizer RSV vaccine during the 365 days pre- or 84 days (as data is available) post-vaccination.
- 6. No code for GBS or its sequalae, in any setting or position, in the 365 days prior to and including ABRYSVO vaccination

There are no exclusion criteria for this analysis.

#### 9.2.3. Variables for Research Question 2

Information about ABRYSVO exposure, GBS, and covariates will be collected from claims data and, as available, state-based IIS data.

## 9.2.3.1. Exposure for Both RCA and SCRI

Exposure to ABRYSVO between 22 October 2024 and the most recent data available at the time of study commencement will be identified in claims data and, as available, state-based IIS data. Receipt of ABRYSVO will be identified using Current Procedural Terminology (CPT) code 90678, vaccine administered code CVX 305, and National Drug Code (NDC) codes 00069-0207-01, 00069-0344-01, and 00069-0344-05. Additional codes for identification of ABRYSVO will be included if relevant codes become available in the future.

#### 9.2.3.2. Outcome

#### **Outcome for RCA**

GBS will be identified in claims data using the algorithm detailed in Table 1. GBS cases will not be confirmed via medical record review for the RCA.

#### 9.2.3.2.1.1. Outcome for Historical Comparator RCA

Follow-up time for GBS in the ABRYSVO-exposed group will start the day after ABRYSVO vaccination and end at the earliest of the following: date of GBS case, 21 days after vaccination, death, or disenrollment.

Follow-up time for GBS in the historical comparator group will start the day after the comparator vaccination and end at the earliest of the following: date of GBS case, 21 days after vaccination, death, or disenrollment.

A second historical comparator RCA will modify the criterion of "21 days after vaccination" for the ABRYSVO-exposed and historical comparator group to "42 days after vaccination."

## 9.2.3.2.1.2. Outcome for Concurrent Comparator RCA

Follow-up time for GBS in the concurrent comparator RCA will start the day after ABRYSVO vaccination and end at the earliest of the following: date of GBS case, 84 days after vaccination, death, or disenrollment.

#### 9.2.3.2.2. Outcome for SCRI

GBS will be identified in claims data using the algorithm detailed in Table 1. This study will include GBS cases during the risk and control windows among people who die during follow-up. Deaths will be captured via enrollment data (for both in-hospital and out-of-hospital deaths) and hospital discharge status (for hospital deaths); death capture is expected to be incomplete, as is typically the case with death data from administrative claims data in the US. Follow-up time will artificially *not* be censored at the time of death. In other words, an eligible individual who has a GBS case during the risk or control windows and dies will still contribute to the full risk and control windows.

If the SCRI study commences due to completion of 4 RSV seasons with no statistically significant positive association between ABRYSVO and GBS from the RCA, GBS cases will not be confirmed via medical record review, but rather results will be adjusted using the PPV of the GBS algorithm produced in Research Question 1. If the SCRI study commences due to a statistically significant finding from an RCA, medical record review of GBS cases in the SCRI study will be conducted as part of the signal evaluation. However, a limitation of medical record review is that not all medical records will be retrievable. For the GBS cases where medical records cannot be retrieved, results will be adjusted using the PPV of the GBS algorithm. For example, if medical records cannot be retrieved for 10 GBS cases and the PPV for the GBS algorithm is 80%, this will be readjusted to 8 GBS cases.

#### 9.2.3.2.2.1. Medical Record Review of Outcome for SCRI

In the scenario of medical record review of GBS cases identified via the SCRI analysis, GBS during the 84 days after ABRYSVO vaccination will be validated, the date of symptom onset identified, and key clinical information abstracted for analysis. The general approach to abstraction and GBS case adjudication outlined in the sections describing the GBS etiology sub-activity of medical record review (Section 9) will be used. Briefly, the medical record associated with the inpatient encounter where GBS was diagnosed will be requested and will serve as the primary focus for adjudication. The record for the first subsequent ambulatory encounter with a neurologist, if applicable, will also be requested. Trained abstractors, or the adjudicators, will extract information from the inpatient and ambulatory records into a database (e.g., REDCap). Information will be collected from sections including admission notes, discharge summaries, laboratory test results, radiographic reports, specialist consultation notes, progress notes, and applicable treatments administered. The abstracted information and corresponding records will be reviewed by a clinician, preferably a neurologist, using study case definitions based on the Brighton Collaboration case definitions for confirmed, possible, and not GBS. The clinician adjudicator will also record the

estimated date that symptoms first appeared per information in the medical record, and this date will be the date used in the final analysis. The GBS onset date is crucial to determining whether the outcome occurred during the risk or control window. Abstractors and adjudicators will be blinded, to the extent possible by redaction, to whether the GBS case occurred in the vaccination risk or control window. Only deidentified data (e.g., relativized dates) will be shared with HPHCI for the analyses. Only aggregate data will be shared externally, including with Pfizer and FDA. Individual-level data will not be shared between RPs or with the study sponsor. Medical records will be obtained from participating RPs in a manner compliant with the Health Insurance Portability and Accountability Act (HIPAA) and local privacy regulations. Hospital charts will be obtained directly through requests from RPs using identifiers obtained from administrative claims data. Designated protected health information users at each RP will link the protected health information with masked patient identification numbers, dates of birth, and provider information for the patients identified for medical chart abstraction.

Notably, medical records will not be 100% obtainable from participating RPs. Section 9.2.7.2. includes a description of how potential events with unobtainable medical records will be handled in the analyses.

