Figure 1. Example design diagram for the self-controlled case crossover design for GBS.

#### 9.1.2. Setting for Research Question 1

GBS will be identified, for all objectives in this protocol, using an algorithm based on Goud and colleagues (2021), which is very similar to other algorithms.  GBS will be defined as incident primary GBS diagnosis (G61.0) in the inpatient setting, or incident GBS in any setting and any position, with a hospitalization within 7 days where GBS is the primary diagnosis. Incidence is defined using 365-day washout for G61.0 or G65.0 in any care setting.

Table 1. Algorithm for incident GBS

ICD-10-CM code	Setting of code	Definition of "incident"	Performance
G61.0 (Guillain- Barré syndrome)	1) G61.0 as primary hospital discharge diagnosis or 2) G61.0 in any position, any setting, followed by a hospitalization within the 7 subsequent days	No evidence of GBS (G61.0 [GBS] or G65.0 [Sequelae of GBS], any setting, any position) in the 365 days	PPV from study using Medicare data: 79%

for which G61.0 was the primary hospital discharge diagnosis.	prior to the first diagnosis code of interest.	(95% CI, 64% - 94%) 
The date of GBS onset will be considered the date of the first eligible G61.0 code in any setting.		

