# 9.2.1.2. Study Design for SCRI

There are 2 scenarios in which the SCRI study may be initiated: 1) if a statistically significant positive association between risk of GBS and ABRYSVO vaccination arises from any RCA, or 2) after 4 RCA seasons, if there was no risk detected. In the former scenario, the SCRI study will serve as refinement of the RCA finding, given the improved control of confounding with the SCRI design, to determine whether a true association exists.

The SCRI design is ideal for studying acute events (e.g., GBS) with well-defined risk periods after a transient exposure.  The incidence of events within a risk window is compared to the incidence of events within a control window. A strength of this design is its ability to control for time-invariant confounders, such as race and age. Time-varying confounders such as seasonality are not controlled unless explicitly accounted for in analyses.

The study population (detailed in Section 9.2.2.2) will be comprised of non-pregnant adults 18-59 years who received an ABYRSVO vaccination from 22 October 2024 (the date of FDA approval of ABRYSVO for adults 18-59 years at increased risk of RSV-LRTD) through the most recent data available at the time of the study commencement, which could include multiple RSV seasons.

The SCRI will compare incidence of GBS during a primary risk window of 1-42 days after ABRYSVO vaccination (day 0 is vaccination) with incidence of GBS during the primary control window 43-84 days after ABRYSVO. The 42-day risk window after vaccine administration for GBS is based upon recent studies that have found days 1-42 post-vaccination to contain the time of increased risk. A secondary risk window of 1-21 days and secondary control window of 43-84 days will also be studied in a sensitivity analysis.

GBS will be identified from claims in all eligible individuals using the algorithm specified in Table 1 during risk and control windows. If the SCRI study is triggered due to a statistically significant finding in the RCA, the GBS cases identified in claims will be confirmed via medical record review as part of the signal refinement process. If the SCRI study commences after 4 seasons without a signal in an RCA, the SCRI study will employ PPV-adjustment of the claims-identified GBS cases.

#### 9.2.2. Setting for Research Question 2

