#### 9.2.7.2.2. Primary Data Analyses

A case-centered logistic regression approach will be used to analyze the data in this SCRI study. Incidence rate ratios with 95% confidence intervals (to estimate relative risk) and attributable risk with 95% confidence intervals per 100,000 doses and 100,000 person-years (to estimate absolute risk) will be calculated.

If the SCRI study is conducted after 3 RCAs (4 seasons) in the absence of a statistically significant finding of higher risk of GBS associated with ABRYSVO vaccination from an RCA, the study will employ PPV-adjustment of the claims-identified GBS cases using the PPVs produced in Research Question 1. If the SCRI study commences due to a statistically significant positive association between risk of GBS and ABRYSVO vaccination in an RCA, the GBS cases identified in claims will be confirmed via medical record review, where medical records could be retrieved. For GBS cases confirmed via medical record review, the date of GBS onset will be determined based on the clinician adjudicator, and the claims-based GBS date will not be used. GBS cases where medical records could not be retrieved will be adjusted based on the PPV of the GBS algorithm. For example, if medical records cannot be retrieved for 10 GBS cases and the PPV for the GBS algorithm is 80%, this will be readjusted to 8 GBS cases. A sensitivity analysis will restrict to chart-confirmed GBS cases.

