## 9.2.7.2.3. Secondary Data Analyses

The following secondary analyses will be conducted for the SCRI:

- 1. A secondary risk window of 1-21 days and secondary control window of 43-84 days will be utilized in a secondary analysis.
- 2. Although the primary study population will not be required to meet the algorithm definition for increased risk of RSV-LRTD, a secondary analysis will restrict to the population who meet the algorithm definition (Table 3).
- 3. A secondary analysis will restrict to chart-confirmed GBS cases.

4. A secondary analysis that assumes different PPVs in the control and risk windows will be conducted, to be detailed in the SAP.

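### The chart-review SCRI finds cases by claims date up to day 84 but assigns them to windows by earlier symptom onset, so late control-window cases are lost and the rate ratio is biased upward

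*Protocol*

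**What the plan says.** Four rules in the protocol combine here.

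- **Case finding.** Section 9.2.1.2: "GBS will be identified from claims in all eligible individuals using the algorithm specified in Table 1 during risk and control windows". Table 1 (section 9.1.2) fixes the claims date: "The date of GBS onset will be considered the date of the first eligible G61.0 code in any setting".
- **Chart review.** Section 9.2.3.2.2.1, for the signal-triggered SCRI: "GBS during the 84 days after ABRYSVO vaccination will be validated, the date of symptom onset identified". Charts are requested with identifiers taken from claims, so a case not found in claims has no chart pulled.
- **Date used in the analysis.** The same section says the adjudicator records the "estimated date that symptoms first appeared per information in the medical record, and this date will be the date used in the final analysis". Section 9.2.7.2.2 repeats that for confirmed cases "the date of GBS onset will be determined based on the clinician adjudicator, and the claims-based GBS date will not be used".
- **Windows.** Section 9.2.1.2 sets the main comparison: "primary risk window of 1-42 days after ABRYSVO vaccination (day 0 is vaccination) with incidence of GBS during the primary control window 43-84 days". Section 9.2.7.2.3 adds: "A secondary risk window of 1-21 days and secondary control window of 43-84 days will be utilized in a secondary analysis".

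No section extends the claims search beyond day 84, allows for a lag or shortens the control window. Section 9.2.3.2.2 credits full windows in its rule for deaths: a case who "dies will still contribute to the full risk and control windows". The limitations in section 9.2.9 do not mention the issue.

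**The concern.** Cases are found on one time scale (first diagnosis code) and classified on another (symptom onset), and onset comes before the code. The day-84 limit on the code therefore acts as an earlier limit on onset, and it cuts only the control window.

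The other boundaries do not offset this. A case coded soon after vaccination with onset before vaccination is correctly removed. A case coded after day 42 with onset by day 42 is correctly moved into the risk window. The only wrong loss is at the end of the control window, so the bias has one direction.

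It matters because section 9.2.1.2 gives this branch the task of refining an RCA finding and settling whether the association is real. An upward bias makes a false signal harder to dismiss.

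**Working it through.** **The plan's own figure.** Section 9.2.5.2 and Table 6 give 7 cases and 2.0 million vaccinees for relative risk 9.7, one-sided alpha 0.05, 80% power, windows 21:42 and a background of 2 per 100,000 person-years.

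- Risk-window share under the null: 21/63 = 0.333. At relative risk 9.7: 9.7/(9.7 + 2) = 0.829.
- Exact binomial, n = 7, reject at 5 or more risk-window cases: alpha 4.5%, power 89.8%. With n = 6 the power is 72.6%, and with n = 5 it is 79.5%. Seven is reproduced.
- Vaccinees: 7 / (0.00002 × 63/365.25) = 2.03 million. This is also reproduced.

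The study size is not in dispute. It supplies the case count and the test used below.

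**Bias in the rate ratio.** Let L be the lag in days from onset to first code. The documents give no value, so 3, 7 and 14 days are assumptions. An onset on days 1-42 is coded by day 84 if L is under 42. An onset in the last L days of days 43-84 is coded after day 84 and lost. The control window yields 42 − L days of cases but is counted as 42, on the assumption that the full-window credit in section 9.2.3.2.2 applies generally. The null rate ratio is 42/(42 − L), the same for 42:42 and 21:42.

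If only a share q of cases has a chart, and the rest stay on their claims date (assumed), the factor is 42/(42 − qL).

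| Assumed L (days) | Control cases lost, L/42 | Factor, all charted | Factor, q = 0.7 (assumed) |
|---|---|---|---|
| 3 | 7% | 1.08 | 1.05 |
| 7 | 17% | 1.20 | 1.13 |
| 14 | 33% | 1.50 | 1.30 |

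Simulated gamma-distributed lags with means of 7 and 14 days gave 1.20 and 1.49. When the claims search ran 60 days longer and cases were then kept by onset in days 1-84, the ratio returned to 1.00.

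**False-positive rate, no true risk, all cases charted.** The risk-window share becomes 42/(84 − L) for 42:42 and 21/(63 − L) for 21:42. Each critical value is the one for L = 0 at one-sided 0.05.

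| Cases, windows | Reject at | L = 0 | L = 3 | L = 7 | L = 14 |
|---|---|---|---|---|---|
| 7, 42:42 | 7 | 0.8% | 1.0% | 1.4% | 2.8% |
| 7, 21:42 | 5 | 4.5% | 5.6% | 7.4% | 12.7% |
| 29, 42:42 | 20 | 3.1% | 4.7% | 8.4% | 21.5% |

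Seven is the planned count at relative risk 9.7, and 29 is the largest count in Table 6. At one-sided 0.025, which corresponds to the lower limit of a 95% interval, 7 cases with 21:42 windows give 0.7%, rising to 0.9%, 1.3% and 2.7%.

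**Cost of a run-out.** Background cases in 42 extra days: 1,000,000 × 0.00002 × 42/365.25 = 2.3 per million vaccinees.

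**The case against.** **The wording could mean onset within 84 days, with the search details left to the SAP.** This does not remove the problem. Section 9.2.1.2 limits claims identification to the windows, so a case coded later would still not be found. The protocol itself fixes both the capture limit and the classification date.

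**The size rests on a lag the documents do not give.** This stands. At 3 days the inflation is 8%, small beside the target relative risks of 2.7 to 9.7. Table 1 also counts a first code in any setting, which can precede the admission and shorten the lag.

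**The reach is limited.** This stands too. Only the signal-triggered branch is affected. The RCAs and the no-signal SCRI find and classify cases on the same claims date. Cases without retrievable charts are kept with PPV weighting and presumably dilute the bias.

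**The stated analysis is estimation with 95% intervals; the one-sided 0.05 test appears only for study size.** This is fair, and the error rates are illustrations. The bias in the estimates does not depend on the test.

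**A reader might infer that a false signal would tend to be confirmed.** The documents do not support that. With 40 null cases and 42:42 windows, the one-sided 0.05 error rate would be 12% at a 7-day lag and 32% at 14 days. Those are raised error rates, not a tendency to confirm, and they do not condition on the RCA signal that triggers this branch. Forty background cases over 84 days also need 40 / (0.00002 × 84/365.25) = 8.7 million vaccinees, against the 2.0 million planned for relative risk 9.7.

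**Conclusion.** The concern holds for the signal-triggered SCRI only. Followed as written, the rules lose control-window cases and bias the incidence rate ratio and attributable risk upward. The direction needs only that symptoms precede the first code, that lags are under 42 days and that the control window is counted in full.

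The size is uncertain. It runs from minor at a 3-day lag to serious at 14 days, applies in full to the chart-confirmed-only analysis and is probably smaller in the primary analysis. At the planned 7 cases, the 42:42 test stays below 5% at all three lags, while the 21:42 test exceeds it. The effect on error rates grows with the number of cases. The point should be corrected because a stated rule gives a biased answer in the analysis meant to judge a signal, and the remedy is cheap.

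**What to change.** In sections 9.2.1.2, 9.2.3.2.2.1 and 9.2.7.2.2, for the chart-review SCRI:

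1. Identify claims cases through day 84 plus a pre-set run-out, for example to day 126, and review those charts.
2. Assign windows by adjudicated onset and keep only onsets on days 1-84.
3. Restrict the analysis to vaccinations with that run-out of data available.
4. State that a case without a chart stays on its claims date and counts only if that date falls in days 1-84.

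The cost is about 2.3 extra background claims cases to review per million vaccinees for a 42-day run-out, and the loss of the most recent vaccinations from this analysis.

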#### 9.2.3.3. Other Variables

Descriptive variables, such as concomitant vaccinations, will be detailed in the SAP.

#### 9.2.3.3.1. Other Variables for RCA

Covariates used for confounding control will be detailed in the SAP and may include age at vaccination, sex, an indicator variable for in and out of season vaccinations, an indicator variable for concomitant vaccinations, and a comorbidity score.

